**Mild and moderate neutropenia:**

A patient who develops mild neutropenia is to continue treatment without interruption, but ANC is to be monitored every 2 days until resolution.

A patient who develops moderate neutropenia is to interrupt treatment as soon as the neutropenia is confirmed, and ANC is to be monitored every 2 days until resolution.

The patient should re-initiate treatment once the event is resolved, defined as 2 consecutive  $ANC \geq 1.5 \times 10^9/L$ . If ANC is still  $< 1.5 \times 10^9/L$  after 14 days, the investigator is to do the following:

- Withdraw patient from the study and monitor him/her until resolution of the event
- Advise patient regarding protective isolation
- Examine patient the same day (if possible), including drug history and physical examination
- Notify ApoPharma Inc. using the SAE form

**Severe neutropenia/agranulocytosis:**

A patient in whom a single ANC measurement  $< 0.5 \times 10^9/L$  is detected is to immediately stop treatment, without waiting for confirmation of the count, and a second measurement is to be done the following day. If the second ANC is still  $< 0.5 \times 10^9/L$ , the patient is to be permanently withdrawn from the study, and ANC is to be monitored daily until resolution. The following procedures should be done by the investigator or the treating physician, as appropriate:

- Provide protective isolation; if clinically indicated, admit patient to hospital and obtain vital signs every 4 hours
- Examine the patient the same day, if possible, including drug history and physical examination
- Notify ApoPharma Inc. using the SAE form.

The following additional measures describe a suggested medical management and monitoring:

- If possible, consider obtaining bone marrow aspirate for:
  - Histology
  - Progenitor culture
  - Frozen storage (1 mL sample)
- If possible, consider obtaining bone marrow biopsy (minimum length 3 mm)
- Perform septic work-up including chest X-ray, blood, urine, and throat cultures
- Obtain q4h temperatures from patient (monitored by family at home if patient is not in the hospital)
- If warranted, administer granulocyte stimulating factors, such as G-CSF 10 µg/kg, on an in-patient basis if possible, beginning the same day that the ANC is confirmed as  $< 0.5 \times 10^9/L$ ; administer daily until ANC is  $> 1.5 \times 10^9/L$  on 2 consecutive days
- If ANC  $< 0.5 \times 10^9/L$  for 7 days, repeat bone marrow biopsy and aspirate weekly during the period of agranulocytosis, if warranted

#### 7.1.1.8.3 Infections

If a patient develops fever ( $\geq 38.5^\circ\text{C}$ ) or symptoms and signs of that indicate systemic infection (e.g., chills, sore throat, mouth ulcers) during the study, deferiprone must be interrupted immediately, and neutrophil count should be obtained and monitored more frequently; every 2 days if ANC is  $< 1.5 \times 10^9/L$ . Therapy with deferiprone can be re-initiated once all symptoms have been resolved and it is deemed safe by the investigator.

#### 7.1.2 Laboratory Measurements

Samples for laboratory safety assessments will be taken at the time points indicated below.

Biochemistry: Total protein, gamma-glutamyl transferase (GGT), lactate dehydrogenase (LDH), sodium, potassium, chloride, glucose, bilirubin (total, direct, and indirect), alanine aminotransferase (ALT), aspartate aminotransferase (AST), albumin, blood urea nitrogen, calcium, creatinine, uric acid, alkaline phosphatase, amylase, serum ferritin, and blood iron	Screening and Days 3, 7, 14, 21, and 28
---	---

Hematology: Hemoglobin, total WBC count, ANC, MCV, and platelet count	Screening, baseline, and Days 7, 14, 21, and 28
Coagulation: Prothrombin Time (PT), Partial Thromboplastin Time (PTT), and International Normalized Ratio (INR)	Screening and Day 2
Serology: HIV Ag/Ab Combo, hepatitis B (HBsAg (B)), and hepatitis C (anti-HCV (C))	Screening
Urinalysis: Color, appearance, specific gravity, pH, leukocyte, protein, glucose, ketones, bilirubin, blood, nitrite, urobilinogen. Microscopic examination must be performed if dipstick test is outside the reference range for leukocyte, blood, nitrite or protein. (Note: For patients with sickle cell disease, samples are to be sent for microscopy if there is blood in the urine or three or more “plus signs” for protein.)	Screening and Day 28
Pregnancy testing: Beta-HCG qualitative serum pregnancy test	Screening and Day 28

**Notes:**

- With the exception of hematology, laboratory results obtained at screening will be treated as the baseline values.
- There will be a window of  $\pm 1$  day for assessments done at Days 3 and 7, and of  $\pm 2$  days for assessments done at Days 14, 21, and 28.
- The investigator may increase the frequency of safety evaluations if deemed appropriate for assessment of any clinically significant adverse event. In the case of increases in liver enzymes that meet the criteria for being considered a safety concern, the patient is to be followed until resolution of the event, beyond Day 28 if necessary.
- If a patient withdraws from the study, the End of Study procedures are to be performed at an early termination visit.

Investigators must document their review of each laboratory report by signing or initialing and dating it. Any laboratory values that fall outside a clinically accepted range, or values

that differ significantly from previous values, must be marked by the investigator as either “CS” (clinically significant) or “NCS” (not clinically significant). Any that are marked as CS must be further explained and documented as an AE.

### **7.1.3 Other Safety Measurements**

#### **7.1.3.1 Physical Examinations**

Physical examination will consist of an examination of head, ears, eyes, nose, throat and neck, respiratory system, cardiovascular system, gastrointestinal system, musculoskeletal system, neurological systems (central and peripheral), and skin, nails, hair, and scalp. A complete examination will be performed at screening, and a symptom-oriented examination will be performed at Day 28. Any abnormalities noted prior to the first dose of study medication will be recorded as either medical history or a medical event (depending on time of occurrence), while any that are noted at the end of the study will be recorded as AEs.

Body weight (without shoes) will be measured at screening only.

#### **7.1.3.2 Vital Signs**

Resting heart rate, resting blood pressure, and body temperature will be taken. Blood pressure should always be measured in the sitting position, after a minimum 3-minute resting period, and using the same arm each time if possible. Systolic and diastolic blood pressures are to be recorded from one measurement.

Vital signs will be measured at screening and Day 28. Clinically significant out-of-range values for vital signs will be reported as AEs (see [Section 7.1.1.1](#)).

#### **7.1.3.3 Concomitant Medications**

The following information about prior and concomitant medications is to be recorded:

- All medications used within the 3 months prior to baseline
- Any medications that the patient continues to take during the study
- Any medications that the patient starts to take during the study

The name, dose, route, frequency, indication, and stop and start dates of all medications used during the study must be noted in the source documents and eCRFs, as well as whether or not the medication was used to treat an AE.

Information on concurrent medications will be obtained at every site visit or telephone contact.

#### **7.1.4 Procedures in Case of Pregnancy**

If a patient becomes pregnant during the course of the study, she will be immediately withdrawn. The pregnancy will be immediately reported to the sponsor, and information about the pregnancy is to be recorded on the appropriate form and in the patient's eCRF. The patient will be followed to determine the outcome, and any premature termination of the pregnancy will be reported. Upon delivery, the child will be examined for any adverse symptoms or congenital anomalies. Follow-up information on the status of the mother and child will be forwarded to the sponsor no later than 8 weeks following the delivery.

If the partner of a male patient becomes pregnant during the course of the study, or if the fetus may have been exposed to the patient's study products either through maternal exposure or through transmission via semen following paternal exposure, the pregnancy must be reported to the sponsor, and information about the pregnancy must be recorded on the appropriate form and in the patient's eCRF. If the partner provides consent for follow-up of the pregnancy, she will be followed until the delivery of the child, and information on the delivery status of the mother and child will be forwarded to the sponsor no later than 8 weeks following the delivery date.

Any SAE occurring as a result of a post-study pregnancy that the investigator believes may have been caused by the study product or by a protocol procedure will be reported to the sponsor as described in [Section 7.1.1.6](#).

#### **7.2 Acceptability Measurements**

On Day 28, following completion of study treatment, patients will be asked what their preference is between the two formulations (Ferriprox IR vs. deferiprone DR) with respect to scheduling, ease of administration, and tolerability. The questionnaire is provided in [Appendix 1](#).

### **8 STUDY COMMITTEES**

A safety committee will be set up that is composed of representatives from ApoPharma Inc. (the Vice President of Medical Affairs, the Director of Medical Safety, and the Director of Clinical Research) and the principal investigators. Other experts may be included as needed. This committee will review the available safety data at specified time points, with a particular emphasis on the number of patients with ALT and/or AST levels that meet the criteria described in [Section 3.1.1.1](#), to confirm if enrollment may continue.

## 9 STATISTICAL ANALYSIS

SAS Windows version 9.3 or higher will be used for statistical analysis. The safety population, defined in [Section 9.3.1](#), will be the primary population for this study.

The continuous and discrete variables for safety data will be summarized with descriptive statistics (mean, median, standard deviation, minimum, and maximum) and frequency tables, respectively, at each assessment.

### 9.1 Endpoints

#### 9.1.1 Primary Endpoint

The primary endpoint is the incidence of any post-dose occurrence of increases in ALT and/or ALT levels that meet one of the criteria for being considered a safety concern. The safety criteria are:

- For a patient whose baseline level is within the normal range, the criterion will be reaching a value of 5 times the ULN during the study.
- For a patient whose baseline level is above the ULN, the criterion will be reaching a value of 5 times the baseline value during the study or  $>10 \times$  ULN.

#### 9.1.2 Secondary Endpoints

Secondary endpoints are as follows:

- The assessment of tolerability will be based on the incidence of gastrointestinal (GI) distress reported by patients during the study.
- The assessment of acceptability will be based on the number of patients who indicate that they prefer the DR formulation over Ferriprox IR after considering their preference with respect to scheduling, ease of administration, and tolerability.

### 9.2 Determination of Sample Size and Study Power

This is the first study of the safety, tolerability, and acceptability of deferiprone DR tablets in patients with systemic iron overload. No formal power calculation can be performed. It is believed that the data that will be obtained in this study will be adequate to evaluate the effect of the DR formulation on liver enzymes.

## **9.3 Study Populations**

### **9.3.1 Safety Population**

The primary analysis population used in this study will be the safety population, which will include all patients who received at least one dose of deferiprone DR tablets.

### **9.3.2 Per Protocol Population**

The per protocol population, which includes all patients who completed the study without major study deviations, will be the secondary population for the assessment of the primary endpoint.

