#### **3.1.1.1 Criteria for Safety Concerns**

As a consequence of liver iron overload and frequent blood transfusions, patients in the target population may have fluctuations of AST and/or ALT that frequently exceed the reference ranges. In recognition of this variability, for each of these enzymes, the criteria for deciding whether an individual patient's increases during the current study is of concern will be set as follows:

- For a patient whose baseline level is within the normal range, the criterion will be reaching a value of 5 times the ULN during the study.
- For a patient whose baseline level is above the ULN, the criterion will be reaching a value of 5 times the baseline value during the study or 10 x ULN.

All cases of patients meeting either of the above criteria at any point during the study must be reported to ApoPharma by the investigator within 24 hours of occurrence, using the sponsor's SAE form.

If at any time during the study a patient's ALT and/or AST values reach a level of **10 x ULN**, do the following:

- If the patient is symptomatic and/or has any other clinically significant abnormal laboratory results, immediately withdraw the patient from the study.
- If the patient is asymptomatic and has no other clinically significant abnormal laboratory results, interrupt treatment and obtain a confirmatory count the next day.
  - If the value is confirmed to be  $\geq 10$  x ULN:
    - Stop treatment, withdraw the patient and complete all end of study assessments scheduled for Day 28
    - Document the event and report it within 24 hours to ApoPharma
    - Monitor the patient daily until the elevated value returns to a level that is regarded as not clinically significant
  - If the confirmatory value is found to be  $< 10$  x ULN, resume treatment as per protocol, and monitor liver enzyme levels within 3 days of resuming therapy.

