#### **4.5 Patient Withdrawal**

Patients have the right to withdraw from the study at any time and for any reason without consequence to future care by the investigator or study center.

A patient may be withdrawn from the study at any time, at the discretion of the investigator, for any of the following reasons:

- Medical or safety reasons considered significant by the patient and/or the investigator
- Requirement for concomitant medication that might interfere with the evaluation of study treatment or may be contraindicated
- Receipt of a rescue medication
- Occurrence of other illnesses that might affect the patient's further participation in the study or evaluation of study treatment
- A protocol deviation that might interfere with study assessments, as judged by the investigator
- Repetitive patient non-compliance with the protocol or with instructions of the investigator
- Participation in another clinical trial at any time during the conduct of this study
- Any other situation where, in the opinion of the investigator, continuation of the study would not be in the best interest of the patient

A patient **must** be withdrawn from the study if any of the following conditions apply:

- Pregnant or planning to become pregnant (see [Section 7.1.4](#))
- A confirmed ALT or AST value  $>10 \times \text{ULN}$  (see [Sections 4.5.1.1](#) and [7.1.1.8.1](#))
- A confirmed ANC value  $< 0.5 \times 10^9$  (see [Sections 4.5.1.2](#) and [7.1.1.8.2](#))
- Occurrence of any adverse event characterized as life-threatening or disabling that is not associated with the patient's condition
- Termination of the study by the sponsor

Patients who decide to withdraw participation in the study should always be contacted, if possible, in order to ask about the reason for withdrawal, whether any adverse events (AEs) occurred, and use of concomitant medications. A withdrawn patient should return for an early termination visit and a follow-up visit. All investigational product and materials should be returned. If any AEs occurred, the investigator must attempt to follow up the outcome until resolution.

If a patient withdraws or is withdrawn before completing the study, the date and reason for the withdrawal must be entered on the source document and on the appropriate page of the electronic case report form (eCRF), and all other appropriate eCRF pages must be completed.

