##### **4.5.1.1 Elevated Liver Enzymes**

A patient who reaches an ALT and/or AST value  $\geq 10 \times \text{ULN}$  at any time during the study is to be **immediately** withdrawn if he or she is additionally symptomatic and/or has any other clinically significant abnormal laboratory results. If there are no other signs of concern, a confirmatory count is to be obtained the next day. If the value is confirmed, the patient is to be withdrawn; if it is not, the patient is to be closely monitored. Details are provided in [Section 3.1.1.1](#).

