## **9.4 Data Analysis Plan**

### **9.4.1 Planned Analyses**

#### **9.4.1.1 Patient Disposition and Drug Exposure**

The number of patients who were exposed to the study medication, who completed the study, and who withdrew from the study will be presented, along with reasons for withdrawals.

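### The per-protocol set admits only completers, so patients withdrawn for an ALT/AST value at about 10 x ULN, itself a primary-endpoint event, drop out of the secondary analysis of that endpoint

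*Combined protocol and SAP*

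**What the plan says.** The analysis sets are defined in section 9.3. The safety population is primary, "which will include all patients who received at least one dose of deferiprone DR tablets" (9.3.1). The per-protocol population is the one "which includes all patients who completed the study without major study deviations, will be the secondary population for the assessment of the primary endpoint" (9.3.2).

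Section 9.1.1 begins: "The primary endpoint is the incidence of any post-dose occurrence of increases in" liver enzymes that meet a safety-concern criterion. For a normal baseline the criterion is 5 x ULN. For a baseline above ULN it is 5 x baseline or a value at about 10 x ULN.

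The withdrawal rules use the upper of these thresholds:

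- Section 3.1.1.1, for a confirmed value in an asymptomatic patient: "Stop treatment, withdraw the patient and complete all end of study assessments scheduled for Day 28". A patient who is symptomatic, or who has other clinically significant laboratory abnormalities, is withdrawn without waiting for confirmation.
- Section 4.5.1.1: "If the value is confirmed, the patient is to be withdrawn; if it is not, the patient is to be closely monitored".
- Section 4.5 lists a confirmed value above 10 x ULN among the reasons for mandatory withdrawal.

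Section 9.4.1.1 reports disposition by counting separately those "who completed the study, and who withdrew from the study will be presented, along with reasons for withdrawals". Section 4.5.3 says that withdrawn patients are not replaced.

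**The concern.** A per-protocol set is meant to exclude patients whose treatment or follow-up departed from the plan. Here it also excludes patients who followed the plan exactly and were withdrawn because the plan told them to stop. The reason for stopping is the outcome being analysed, so membership of the set depends on the endpoint, and the events removed are the most severe ones.

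At stake is the plan's second estimate of its primary safety endpoint, in the first study of this formulation in iron-overloaded patients. With 15 patients per group, one or two such exclusions visibly change the rate. A reader who takes the per-protocol figure as support for the safety-population figure would be relying on a number from which the worst cases had been removed.

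**Working it through.** **1. Is every withdrawal at about 10 x ULN an endpoint event?** Write baseline b in multiples of ULN.

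- Normal baseline: the event threshold is 5, so a value at 10 is an event.
- Baseline above 1 and up to 2: the event threshold is 5b, which is at most 10, so a value above 10 is an event.
- Baseline above 2 and up to 5 (eligible, because section 4.3 excludes only values above 5 x ULN): 5b exceeds 10, so the 10 x ULN limb is reached first. Event and withdrawal thresholds coincide. In this stratum a confirmed event before study end leads to withdrawal.

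There is one boundary gap. Sections 3.1.1.1 and 4.5.1.1 act at 10 x ULN or at and above it, while 4.5 and 9.1.1 say above 10 x ULN. A value of exactly 10 x ULN in a patient with b above 2 would be a withdrawal under 3.1.1.1 but not an event under 9.1.1.

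**2. Is a withdrawn patient a completer?** Section 9.4.1.1 counts completion and withdrawal as separate categories, and section 4.5 refers to patients withdrawn before completing the study. Nothing in 9.3.2 keeps a patient who was withdrawn for an endpoint event.

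**3. Direction.** Let e of n patients have events, with k of the event patients withdrawn. As written, the per-protocol rate is (e − k)/(n − k). This is below e/n for any k ≥ 1 with e < n. For a given set of other exclusions, the rule can therefore only lower the rate. Exclusion of event-free patients raises it, so the net difference from the safety population can go either way.

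**4. Size.** The plan gives no expected event rate and no power calculation (section 9.2), so there is no figure to reproduce. The counts below are assumptions. The intervals are exact Clopper-Pearson 95% limits, the method named in 9.4.1.3.

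| Assumed situation in one group of 15 | Safety population | Per-protocol as written |
|---|---|---|
| 1 event, withdrawn | 1/15 = 6.7% (0.2–31.9) | 0/14 = 0.0% (0.0–23.2) |
| 3 events, 1 withdrawn | 3/15 = 20.0% (4.3–48.1) | 2/14 = 14.3% (1.8–42.8) |
| 3 events, 2 withdrawn | 3/15 = 20.0% (4.3–48.1) | 1/13 = 7.7% (0.2–36.0) |
| 3 events, 1 withdrawn, plus 2 event-free withdrawals | 3/15 = 20.0% (4.3–48.1) | 2/12 = 16.7% (2.1–48.4) |

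In the last row, keeping the withdrawn event patient would give 3/13 = 23.1% (5.0–53.8).

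**5. How likely is it?** With probability p per patient, the chance of at least one such withdrawal in 15 is 1 − (1 − p)^15:

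- p = 5/889 (liver-enzyme discontinuations in the sponsor's deferiprone trials, section 1.2): 8.1%
- p = 2% (assumed): 26.1%
- p = 5% (assumed): 53.7%

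The chance of two or more in one group is 0.3%, 3.5% and 17.1% respectively.

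**The case against.** The strongest case against is that little depends on this set. The safety population is primary and keeps every such patient. The primary endpoint has no hypothesis test, and enrollment decisions use raw counts of patients meeting the criteria (sections 3.1.1.2 and 8). The omission would also be visible: withdrawals are tabulated with reasons, and each case goes to the sponsor within 24 hours. This stands, and it limits the weight of the point. It does not make the secondary estimate sound.

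Second, completion is not formally defined, and 3.1.1.1 has the withdrawn patient undergo the Day 28 assessments early, which might be called completion. Sections 4.5 and 9.4.1.1 point the other way. If the sponsor intends the generous reading, 9.3.2 should say so.

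Third, such events may be rare. In LA60-0118 (section 1.1) about 20% of the healthy volunteers dosed to that point reached roughly 5 x ULN and one reached 8 x ULN; no value of 10 x ULN is reported. Events below 10 x ULN, unconfirmed values in asymptomatic patients and values first seen at Day 28 may all stay in the set. The 5/889 figure is only a proxy for confirmed values on DR over 28 days. All of this is fair. But those volunteers were not the target population, and the rate in patients is unknown.

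Fourth, keeping withdrawn patients with events while omitting early dropouts without them is also outcome-dependent, and it tilts the rate upward: 3/13 = 23.1% in the example, against 3/15 = 20.0% in the safety population. That is true. The justification is that an any-occurrence outcome is fully observed once the event has happened, whereas for an event-free early dropout it is not. For a safety endpoint this is also the cautious direction.

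**Conclusion.** The concern holds. Applied as written, 9.3.2 together with the mandatory withdrawal rules removes the most severe primary-endpoint events from the secondary analysis of that endpoint. This should be fixed, but it does not touch the primary safety-population analysis.

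The conclusion rests on reading a withdrawn patient as a non-completer, which the text supports. The size depends on assumed event counts: each event-driven withdrawal in a group of 15 lowers the per-protocol rate by about 6 to 7 percentage points in the illustrations (20.0% to 14.3% to 7.7%, or 6.7% to 0%), with wide and overlapping intervals. The extra withdrawals described in 3.1.1.2 add to the loss only if 4 or more of 10 patients in a group meet the criterion.

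**What to change.** In section 9.3.2 keep the completion and no-major-deviation requirement and add:

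> Patients who met the primary-endpoint criterion before withdrawal, with no major deviation up to that point, are included and counted as events.

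Early dropouts without an event stay out. If nobody else were excluded, the per-protocol estimate would then equal the safety-population estimate. Alternatively, drop the per-protocol analysis for this endpoint, which also avoids the upward tilt noted above.

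Separately, reconcile the wording of the 10 x ULN threshold across sections 3.1.1.1, 4.5, 4.5.1.1 and 9.1.1, so that it is clear which withdrawn patients count as events.

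The cost is one sentence and no new data, and the added sentence changes no clinical rule. The per-protocol rate may be less favourable than under the present definition.
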